#### 9.2.3.5 Analysis of the Supportive Estimands

The supportive estimand of death will be analysed using the same methods as progression to severe disease or death, as detailed in [Section 9.2.1.2](#).

**Statistical Analysis Plan (RotW)**

Final v1.0, 08FEB2022

SG018

**9.3 Secondary Efficacy Endpoints****9.3.1 Secondary Estimands**

The estimands for the secondary endpoints are defined in table 23.

**Table 23: Secondary estimand definitions**

Endpoint	Population of interest	Consideration of intercurrent events	Summary measure
Proportion of recovered patients at days 7, 14, 21 and 28	ITT	
Composite variable: Subjects who die cannot recover, death after recovery will be considered as a rebound.
 
Treatment policy: Regardless of protocol deviations, treatment adherence and any concomitant therapies received for the treatment of SARS-CoV-2.
 
While on study: Recovery will be determined at study withdrawal, if withdrawal occurs prior to day 35.
	Difference in proportions for each SNG001 arm versus placebo at each day
	Per Protocol	Hypothetical: Estimand for a situation with treatment compliance and no protocol deviations affecting efficacy.	
Proportion of patients discharged from hospital at days 7, 14, 21 and 28	ITT	
Composite variable: Subjects who die cannot be discharged, death after discharge will be considered as a rebound.
 
Treatment policy: Regardless of protocol deviations, treatment adherence and any concomitant therapies received for the treatment of SARS-CoV-2.
 
While on study: Discharge will be determined at study withdrawal, if withdrawal occurs prior to day 35.
	Difference in proportions for each SNG001 arm versus placebo at each day
	Per Protocol	Hypothetical: Estimand for a situation with treatment compliance and no protocol deviations or prior medications affecting efficacy.	
Improvement across the entire OSCI scale at days 7, 14, 21 and 28	ITT	
Composite variable: Death is defined by an OSCI score of 8.
 
Treatment policy: Regardless of protocol deviations, treatment adherence and any concomitant therapies received for the treatment of SARS-CoV-2.
 
While on study: OSCI scores following study withdrawal will be considered missing.
	Odds ratio for each SNG001 arm versus placebo at each day
	Per Protocol	Hypothetical: Estimand for a situation with treatment compliance and no protocol deviations affecting efficacy.	
Change in total BCSS score over the study period	ITT	Treatment policy: Regardless of protocol deviations, treatment adherence and any concomitant therapies received for the treatment of SARS-CoV-2.	Difference in LS means between each SNG001 arm versus placebo

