8.5.5 Handling of Missing Data

For analyses using the WHO OSCI, including the primary and key secondary endpoints, patients with a WHO OSCI score of 8, indicating death, will have any subsequent missing WHO OSCI assessments imputed as 8. In addition, if other data sources such as AEs indicate a patient has died all missing WHO OSCI scores on and after the date of death will be imputed as 8.

For relevant analyses, missing WHO OSCI assessments for patients who withdraw from the study alive will be imputed using multiple imputation under a missing at random assumption. Selected analyses will be repeated using a missing not at random approach through an imputation model estimated from patients in the placebo group.

For the mixed models with repeated measures (MMRM) of breathlessness, missing breathlessness scores will be imputed as 4 if the WHO OSCI score at the corresponding visit is ≥ 5 . Cough and sputum scores at corresponding visits will be considered missing at random and total BCSS scores will be calculated by summing the imputed symptom scores, where possible. Missing breathlessness, cough and sputum scores at all other visits will be considered missing at random and will not explicitly be imputed but will be accounted for by the MMRM analysis. Missing not at random approaches may also be considered for sensitivity analyses.

Further details regarding missing data approaches will be given in the SAP.

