## 7.3 Missing Data

### 7.3.1 OSCi

#### 7.3.1.1 General Imputation Rules

For analyses using the OSCi, including the primary and key secondary endpoints, subjects with an OSCi score of 8, indicating death, will have any subsequent missing OSCi assessments set as 8. In addition, if other data sources such as AEs indicate a patient has died all missing OSCi scores on and after the date of death will be set as 8. Any missing baseline OSCi scores will be imputed as 4, as per the study inclusion criteria.

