#### **9.2.1.3 Sensitivity Analyses of the Key Secondary Estimand**

The sensitivity of the key secondary analysis to missing data due to withdrawal from study prior to progression to severe disease or death will be assessed firstly through a tipping point analysis for a range of sensitivity parameters,  $\delta_i$ , for each  $i^{\text{th}}$  patient.  $\delta_i$  represents the change to the odds of severe disease or death. If  $\delta_i$  is set to 1 this will represent a Missing at Random (MAR) approach, if  $\delta_i < 1$  the imputed OSCi score will be lower than that of the MAR approach and progression to severe disease will be less common. If  $\delta_i > 1$  the imputed OSCi score will be higher than that of the MAR approach and progression to severe disease will be more common. Values of  $\delta$  will be varied independently for each treatment group.

Missing data will be imputed in M datasets. OSCi will be considered a categorical variable and the imputation algorithm will use a monotone logistic regression method to impute missing OSCi scores. Each of the covariates used in the primary analysis, including treatment group, will be included as covariates in the logistic regression. Missing data will be imputed iteratively by day, starting at day 2. For each subsequent day, the OSCi scores at prior days will be included as covariates, including the OSCi scores imputed in earlier iterations. This will not include the OSCi score at day 1 because this will always be 4, by design. However, because there are 34 scheduled visit days to be imputed in this way it is likely as the imputation progresses that the imputation model will become over-parameterised. To avoid this issue and to account for the fact that the most recent days are most likely to be predictive, only the OSCi score at the previous two days will be used as continuous covariates. Any imputations of 8 (death) will be “carried forward” to all future missing days after each step and not imputed again.

For each imputed dataset and for each value of  $\delta_i$  the primary analysis method will be repeated. The estimates from the imputed datasets will be combined for each value of  $\delta_i$  using Rubin’s rules. The results for the different combinations of  $\delta_i$  for Placebo and SNG001 patients will be plotted on a heat map to identify, if applicable, where the p-values becomes insignificant. This ‘tipping point’ will also be tabulated along with specific values of  $\delta_i$ .

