### 9.3.2 Analysis of Secondary Estimands

#### 9.3.2.1 Recovery at days 7, 14, 21 and 28

Logistic regression models will be applied to OSCi recovery by days 7, 14, 21 and 28. For recovery by visit a patient will be considered recovered at every visit following the first confirmed recovery. E.g. a patient who recovers at Day 6 will be considered recovered at Days 7, 14, 21 and 28 regardless of what happens after the confirmed recovery.

Covariates will be included in the logistic regression model as per [Section 7.2](#).

The number and percentage of patient who recovered within each treatment group will be presented with the difference in the proportions of patients who recovered between the treatment groups alongside the odds ratios, 95% CI of the odds ratios and p-value from the logistic regression.

If quasi-complete separation of a covariate occurs at any visit the Firth logistic regression method will be used across all visits to avoid using maximum likelihood estimation when calculating the estimates.

The odds ratios for recovery, hospital discharge and improvement across the entire OSCi scale by days 7, 14, 21 and 28 in SNG001 versus placebo and their corresponding 95% CI and p-values will be presented in a forest plot, in which the x-axis will represent the odds ratios and the y-axis will stand for the estimates of the above mentioned secondary endpoints.

The same analysis methods will be used to use to assess both of the estimands in [Section 9.3.1](#).

#### 9.3.2.2 Hospital discharge at days 7, 14, 21 and 28

Hospital discharge by days 7, 14, 21 and 28 will be assessed using the same methods as recovery at days 7, 14, 21 and 28, as described in [Section 9.3.2.1](#).

#### 9.3.2.3 Improvement across the entire OSCi scale at days 7, 14, 21 and 28

Improvement across the entire OSCi scale at days 7, 14, 21 and 28 will be analysed through an ordered logistic regression model, assuming proportional odds across the treatment groups.

Covariates will be included in the logistic regression model as per [Section 7.2](#).

The odds ratios will be presented for each visit alongside their 95% CIs and p-values.

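### The ordinal OSCI models at Days 7, 14, 21 and 28 leave out patients who withdrew alive but keep known deaths, and the SAP neither explains this nor tests it

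*SAP*

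**What the plan says.** **Withdrawal and death in the ordinal estimand.** The ITT row of SAP Table 23 for improvement across the whole scale says: "While on study: OSCI scores following study withdrawal will be considered missing". The same row says: "Composite variable: Death is defined by an OSCI score of 8".

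**The model.** Under SAP 9.3.2.3 the endpoint "will be analysed through an ordered logistic regression model, assuming proportional odds across the treatment groups", with results shown for each visit. No imputation is mentioned. The only sensitivity analysis in that section re-derives scores 0 and 1 from the symptom assessments. SAP Table 7 also plans the model for the per protocol population and the subgroups.

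**Missing scores in general.** SAP 7.3.1.1 provides that patients with a score of 8, "indicating death, will have any subsequent missing OSCi assessments set as 8". It applies the same rule "if other data sources such as AEs indicate a patient has died all missing OSCi scores on and after the date of death". SAP 7.3.1.2 and 7.3.1.3 then cover time-to-event and binary endpoints only.

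**The protocol.** Section 8.5.5 says: "For relevant analyses, missing WHO OSCI assessments for patients who withdraw from the study alive will be imputed using multiple imputation", under a missing-at-random (MAR) assumption. It leaves further detail to the SAP.

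**An OSCI imputation already in the SAP.** In 9.2.1.3, for the key secondary sensitivity analyses, "the imputation algorithm will use a monotone logistic regression method to impute missing OSCi scores". It runs day by day from Day 2, carries imputed deaths forward, and is MAR when delta is 1.

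**Changes from the protocol.** SAP Section 15 does not mention the handling of withdrawn patients in the ordinal analysis.

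**The concern.** Read together, these passages make the ordinal analysis a complete-case analysis among survivors. A patient who withdrew alive before a visit has no score and cannot enter that visit's model, while a patient known to have died enters at every later visit. A survivor who misses only the target-day assessment would apparently be dropped too; that is inferred from the SAP's silence and cannot be sized from the documents.

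The while-on-study label does not fit. In the recovery and discharge rows of the same table, the same label means that status is determined at withdrawal, so those patients stay in. SAP 9.3.2.1 puts all three sets of odds ratios in one forest plot, so neighbouring Day 28 estimates would rest on different sets of patients.

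Three things are at stake:
- **Precision.** Daily scores up to withdrawal, which should help to predict the later category, go unused.
- **The displayed distribution.** The analysed patients contain too large a share of deaths.
- **The odds ratio.** It is exposed if withdrawal differs by arm. The primary and key secondary endpoints have tipping-point and reference-based analyses for withdrawal; this endpoint has none.

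**Working it through.** **Inputs from the documents.** N = 610, 1:1; dropout 25% over 28 days, exponential; placebo discharge 70% and recovery 30% at Day 28 (Protocol 8.1).

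**Inputs assumed.** Mortality of 5%, death times uniform over 28 days, and the Day 28 distribution and withdrawal patterns in step 5. The documents give none of these.

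**1. The plan's own figure.** No power is stated for the ordinal endpoint; the stated figure that bears on it is the dropout. The daily hazard is w = −ln(0.75)/28, so the share withdrawn by day D is m = 1 − 0.75^(D/28), which is 25% at D = 28. The same dropout model, with hazard ratios of 1.45 and 1.7, gives about 418 discharge and 202 recovery events. Schoenfeld power at two-sided 0.025 is then 94.0% and 93.7%, in line with the stated minimum of 90%.

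**2. Patients lost and cost in precision.** If imputation recovered everything, the standard error (SE) ratio would be 1/√(1 − m), which is therefore an upper bound. The last two columns assume that 5% die and all deaths are retained, so the loss is 0.95 × m. Using the full 5% at the earlier days makes those rows a low end.

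| Day | m | of 610 | SE ratio | 0.95 × m | SE ratio |
|---|---|---|---|---|---|
| 7 | 6.9% | 42 | 1.037 | 6.6% | 1.035 |
| 14 | 13.4% | 82 | 1.075 | 12.7% | 1.070 |
| 21 | 19.4% | 118 | 1.114 | 18.4% | 1.107 |
| 28 | 25.0% | 152 | 1.155 | 23.75% | 1.145 |

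At Day 28 the model would use about 458 patients (610 − 152), or about 465 if all deaths are retained (610 × 0.7625).

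**3. Share of deaths at Day 28, true mortality 5%.**
- All deaths known: 0.05/(0.05 + 0.95 × 0.75) = 0.05/0.7625 = 6.6%.
- Only deaths before withdrawal known: the fraction seen is 0.25/(−ln 0.75) = 0.869, so 0.869 × 0.05 = 0.0435 and 0.0435/(0.0435 + 0.7125) = 5.8%.

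**4. Patients still in hospital at Day 28.**
- Withdrawal unrelated to status among survivors (5% dead, 70% discharged, 25% in hospital): 0.25 × 0.75/0.7625 = 24.6%, slightly below the true 25%.
- Withdrawal only after discharge, on the step 5 distribution (8% dead, 70% discharged, 22% in hospital): a quarter of survivors is 0.25 × 0.92 = 0.23, all taken from the discharged, so 0.22/0.77 = 28.6% against a true 22%.

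**5. Odds ratio with no true effect.** A large-sample proportional-odds fit was run on an assumed Day 28 distribution for scores 0 to 8 of 15, 15, 40, 5, 10, 3, 2, 2 and 8%. All deaths were kept and withdrawal was applied to survivors. The odds ratio is for a worse score on SNG001.

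| Withdrawal, SNG001 v placebo | Unrelated to status among survivors | Only after discharge |
|---|---|---|
| 25% v 25% | 1.00 | 1.00 |
| 20% v 30% | 0.96 | 0.86 |
| 15% v 35% | 0.92 | 0.74 |

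**The case against.** The strongest reply concerns the protocol. Its imputation sentence is limited to relevant analyses and does not name the ordinal model. Its main OSCI analyses do not impute: the primary endpoints censor, and the key secondary estimand is while-on-study, with imputation only in sensitivity analyses. The sentence can be read as meaning those sensitivity analyses, which the SAP keeps, and on that reading Section 15 had nothing to declare. This stands. A reader might infer that the SAP contradicts the protocol, but the wording does not support that. What remains is a gap: the ordinal model takes the OSCI score itself as its outcome, and if it is not a relevant analysis the SAP should say so.

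Other limits also stand:
- **Deaths.** It is tempting to say that deaths are always kept. Only known deaths are. After withdrawal, SAP 7.3.1.1 needs another data source, and SAP Table 20 counts later deaths for the mortality endpoint only if consent is received.
- **Patients in hospital.** A reader might infer that they too are over-represented. Step 4 shows that this needs withdrawal concentrated after discharge. SAP Table 8 expects withdrawal soon after discharge to reflect lack of interest or time, which makes the pattern plausible but does not establish it.
- **Bias.** The arm imbalances in step 5 are assumptions. Protocol 8.4.1 expects withdrawal to be independent of the treatment effect.
- **Ready-made imputations.** The 9.2.1.3 model is aimed at withdrawal before progression. The text does not show that it covers patients who progressed and then withdrew, or intermittent gaps, and patients with baseline OSCI of 5 or more are excluded from the severe-disease analyses (SAP 5.3.1.3).

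**Conclusion.** The point holds as a gap in a secondary analysis. As written, the ordinal models drop patients who withdrew alive before the visit and keep known deaths. The label does not match its use in the neighbouring rows, and no sensitivity analysis tests the choice.

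At the planned dropout, the losses are up to about 7%, 13%, 19% and 24–25% of patients at the four days. The standard error is inflated by at most about 4%, 7–8%, 11% and 15%. Imputation would recover only part of this, and how much cannot be told from the documents. The death share at Day 28 would be overstated modestly, at 5.8–6.6% for an assumed true 5%.

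A reader might conclude that the treatment effect is biased as planned. The documents do not show that. With withdrawal equal by arm, the null odds ratio stays at 1.00. It moves if withdrawal differs by arm, and moves further if withdrawal is also tied to status. The plan has no analysis that would reveal this for the ordinal endpoint.

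The endpoint is outside the testing hierarchy in SAP 7.6, so the primary and key secondary conclusions are unaffected.

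**What to change.** In SAP Table 23 and 9.3.2.3:
- Fit the four proportional-odds models on multiply imputed OSCI data, using the day-by-day model of 9.2.1.3 with delta = 1, and combine the results with Rubin's rules.
- Extend that imputation to all ITT patients, including those who progressed before withdrawing, those with baseline OSCI of 5 or more, and those with intermittent gaps.
- Keep the complete-case fit as a sensitivity analysis.
- Relabel the withdrawal strategy to match, as treatment policy; 9.2.1.3 already describes its own imputation analyses that way.

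If the sponsor prefers complete cases as the main analysis, the minimum is to say so in 9.3.2.3, give the reason in Section 15, and add the MAR fit as a sensitivity analysis.

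The cost is modest extra programming and a short SAP edit. The main estimate would then rest on MAR given the observed scores and covariates, an assumption that should be stated.

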## Statistical Analysis Plan (RotW)

Final v1.0, 08FEB2022

SG018

			averaged over the whole study period
Change in breathlessness score over the study period	ITT	Treatment policy: Regardless of protocol deviations, treatment adherence and any concomitant therapies received for the treatment of SARS-CoV-2.	Difference in LS means between each SNG001 arm versus placebo
	Per Protocol	Hypothetical: Estimand for a situation with treatment compliance and no protocol deviations affecting efficacy.	averaged over the whole study period
Change in cough score over the study period	ITT	Treatment policy: Regardless of protocol deviations, treatment adherence and any concomitant therapies received for the treatment of SARS-CoV-2.	Difference in LS means between each SNG001 arm versus placebo
	Per Protocol	Hypothetical: Estimand for a situation with treatment compliance and no protocol deviations affecting efficacy.	averaged over the whole study period

### 9.3.2 Analysis of Secondary Estimands

#### 9.3.2.1 Recovery at days 7, 14, 21 and 28

Logistic regression models will be applied to OSCi recovery by days 7, 14, 21 and 28. For recovery by visit a patient will be considered recovered at every visit following the first confirmed recovery. E.g. a patient who recovers at Day 6 will be considered recovered at Days 7, 14, 21 and 28 regardless of what happens after the confirmed recovery.

Covariates will be included in the logistic regression model as per [Section 7.2](#).

The number and percentage of patient who recovered within each treatment group will be presented with the difference in the proportions of patients who recovered between the treatment groups alongside the odds ratios, 95% CI of the odds ratios and p-value from the logistic regression.

If quasi-complete separation of a covariate occurs at any visit the Firth logistic regression method will be used across all visits to avoid using maximum likelihood estimation when calculating the estimates.

The odds ratios for recovery, hospital discharge and improvement across the entire OSCi scale by days 7, 14, 21 and 28 in SNG001 versus placebo and their corresponding 95% CI and p-values will be presented in a forest plot, in which the x-axis will represent the odds ratios and the y-axis will stand for the estimates of the above mentioned secondary endpoints.

The same analysis methods will be used to use to assess both of the estimands in [Section 9.3.1](#).

#### 9.3.2.2 Hospital discharge at days 7, 14, 21 and 28

Hospital discharge by days 7, 14, 21 and 28 will be assessed using the same methods as recovery at days 7, 14, 21 and 28, as described in [Section 9.3.2.1](#).

#### 9.3.2.3 Improvement across the entire OSCi scale at days 7, 14, 21 and 28

Improvement across the entire OSCi scale at days 7, 14, 21 and 28 will be analysed through an ordered logistic regression model, assuming proportional odds across the treatment groups.

Covariates will be included in the logistic regression model as per [Section 7.2](#).

The odds ratios will be presented for each visit alongside their 95% CIs and p-values.

If quasi-complete separation occurs due to low incidence of some OSCi levels then neighbouring OSCi levels may be pooled for the purpose of the analysis to a minimum of two levels ( $\leq 3$  and  $\geq 4$ ), in which case the analysis will simplify to a binary logistic regression. Also, covariates may be dropped from the analysis if it is clear that the cause of quasi-complete separation is a particular categorised covariate.

The proportional odds assumption will be tested by re-running the ordered logistic regression model with both unequal and equal slopes for the treatment effect and equal slopes for all other covariates.

Proportionality will be assessed by the statistical significance of the treatment effect for unequal slopes, at the 5% significance level.

The same analysis methods will be used to use to assess both of the estimands in [Section 9.3.1](#).

A sensitivity analysis of the estimand using the ITT population will be performed where OSCi levels of 0 and 1 will be derived based on the COVID-19 symptom assessments. An OSCi score of 0 will be assigned if no COVID-19 symptoms are present, regardless of the OSCi score recorded in the clinical database. An OSCi score of 1 will be assigned if any COVID-19 symptoms are present and an OSCi score of 0 was recorded in the clinical trial database. The number and percentage of patients with a rederived OSCi score will be presented at each time point along with the odds ratios and their 95% CIs and p-values.

The number and percentage of patients with each OSCi score at each post baseline visit will also be presented.

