8.5.3 Analysis of Secondary Efficacy Endpoints

All analyses of secondary endpoints described below will include the covariates used for the primary analysis, unless stated otherwise.

Recovery and hospital discharge will be analysed at Days 7, 14, 21 and 28 using a logistic regression model to determine the difference in proportions for SNG001 versus placebo.

Improvement on the WHO OSCI scale will be analysed at Days 7, 14, 21 and 28 assessed using an ordered logistic regression model assuming proportional odds to estimate the odds ratios for SNG001 versus placebo. Adjacent WHO OSCi categories may be merged for some or all visits if the outcome frequency for some WHO OSCI levels is low for any treatment arm.

Observed WHO OSCI scores will also be summarised descriptively.

Change from baseline in breathlessness and cough scores according to the BCSS and total BCSS score will be assessed using a mixed model for repeated measures. The difference between SNG001 and Placebo across the treatment period (up to Day 14) will be estimated alongside the 95% CIs and p-values. The covariates used for the primary analysis will be used with an additional covariate for baseline score.

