## Statistical Analysis Plan (RotW)

Final v1.0, 08FEB2022

SG018

- High (> 66th percentile)

The following variables are factors of interest which have been selected so show homogeneity of the treatment effect:

- COVID-19 Related Therapy at randomisation
  - Remdesivir by any route
  - Corticosteroids by any systemic route (Dexamethasone, Methylprednisolone, Prednisolone, Hydrocortisone)
  - Dexamethasone by any route
  - Dexamethasone administered orally
  - Dexamethasone administered intravenously
- All cases of the above medication use will be included, regardless of whether indicated for COVID-19 or a comorbidity.
- SNG001 Manufacturing Batch
  - SNG001 manufactured using [REDACTED] derived material
  - SNG001 manufactured using [REDACTED] derived material.

The following covariates will be included in statistical models:

- Age as a continuous variable
- Sex:
  - Male
  - Female
- Prior duration of symptoms as a continuous variable
- Geographic region (See [Section 7.5](#))
- COVID-19 vaccine status at randomisation:
  - No prior COVID-19 vaccination
  - Partially vaccinated
  - Fully vaccinated

Patients who receive different types of COVID-19 vaccination will be pooled into a single subgroup.

Only subgroups with at least 20 patients in total will be included in any summaries or analyses.

For analyses of change from baseline for variables other than OSCI the baseline value will also be included as a covariate.

For subgroup analyses the subgroup variable will not be included in the models. The study has not been powered for any of the subgroups defined above, therefore all subgroup analyses should be considered exploratory.

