**Table 7: Planned efficacy analyses**

Planned Analysis	ITT	PP	Subgroups of the ITT
Cox proportional hazards analysis of time to hospital discharge	X	X	X 
Cox proportional hazards analysis of time to recovery	X	X	X 
Kaplan Meier analysis of time to hospital discharge	X	X	X 
Kaplan Meier analysis of time to recovery	X	X	X 
Logistic regression analysis of severe disease or death within 35 days of first dose	X	X	X 
Logistic regression analysis of intubation or death within 35 days of first dose	X	X	X 
Logistic regression analysis of death within 35 days of first dose	X	X	
Logistic regression analysis of recovery at days 7, 14, 21 and 28	X	X	
Logistic regression analysis of hospital discharge at days 7, 14, 21 and 28	X	X	
Proportional odds analysis of improvement on the OSCI scale at days 7, 14, 21 and 28	X	X	X
Mixed model for repeated measures (MMRM) analysis of BCSS total score	X		
MMRM analysis for breathlessness and cough scores	X	X	X

Analysis will only be performed if sufficient events occur within the analysed population.

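### Pooling OSCI outcome levels, as SAP 9.3.2.3 allows, cannot remove separation in the equal-slopes proportional-odds model

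*SAP*

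**What the plan says.** Improvement on the OSCI at Days 7, 14, 21 and 28 "will be analysed through an ordered logistic regression model, assuming proportional odds across the treatment groups" (SAP 9.3.2.3). Each covariate, including treatment, therefore has one slope across all cut-points.

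The same section gives the rule for separation: "If quasi-complete separation occurs due to low incidence of some OSCi levels then neighbouring OSCi levels may be pooled". The pooling may go as far as 3 or below against 4 or above, "in which case the analysis will simplify to a binary logistic regression". The next sentence also lets a categorised covariate be dropped if it is clearly the cause. SAP 7.5 lets Latin America be combined with India if sparse recruitment causes problems such as non-convergence.

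For the binary recovery and discharge endpoints the remedy differs: "If quasi-complete separation of a covariate occurs at any visit the Firth logistic regression method will be used across all visits" (SAP 9.3.2.1, applied to discharge by 9.3.2.2). SAP 9.3.2.3 names no Firth option for the ordinal model or for the binary model it may become.

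Protocol 8.5.3 has a looser rule that does not mention separation: "Adjacent WHO OSCi categories may be merged for some or all visits if the outcome frequency for some WHO OSCI levels is low".

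The row "Proportional odds analysis of improvement on the OSCI scale at days 7, 14, 21 and 28" in SAP Table 7 is marked for ITT, per protocol and subgroups. It lacks the footnote, carried by the primary-endpoint rows, that requires sufficient events. SAP 7.2 sets the only size limit: "Only subgroups with at least 20 patients in total will be included in any summaries or analyses".

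**The concern.** The rule attributes separation to rare outcome levels and treats it by merging them. In a model with one slope per covariate, separation comes from the covariates: some combination of them ranks patients with no contradiction to the outcome order. A sparse covariate level is the usual source. Merging outcome levels leaves that source untouched.

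At stake is an endpoint meant to use the whole scale. An analyst who meets separation and follows the pooling clause would still have separation and could merge further. At the permitted limit, low-flow oxygen (4) and death (8) become the same outcome. The protocol wording also lets the merging differ between visits, so odds ratios on different scales could appear side by side in the forest plot described in SAP 9.3.2.1.

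**Working it through.** The documents give no figure for this rule, so there is none to reproduce.

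**1. When the estimate is infinite.** Write the model as logit P(Y ≤ k) = θ_k − x'β. With full-rank covariates and only observed levels kept, the slope estimate is infinite if and only if some d ≠ 0 and threshold shifts δ satisfy, for every patient at level y,

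δ_(y−1) ≤ x'd ≤ δ_y.

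In words: nobody at a lower level has a higher score x'd than anybody at a higher level.

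**2. What pooling does.** Merging levels k and k+1 deletes δ_k and every inequality containing it, and adds none. Any d that separated before still separates. A d that was blocked only by the deleted inequalities now separates too.

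**3. Small cases.** The reference group has counts 30, 60, 120, 25, 25, 15, 6, 6, 18 over levels 0 to 8.

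| Comparison group | Full scale | After ≤3 v ≥4 |
|---|---|---|
| Other arm, level 8 empty (40, 70, 115, 22, 22, 14, 14, 8, 0) | not separated | not separated |
| Covariate group of 6, all at level 0 | separated | separated |
| Covariate group of 6, spread 1, 2, 2, 1 over levels 0 to 3 | not separated | separated |

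The first row is the situation the SAP blames, and it causes no separation. The second is real separation, and the cut does not cure it. The third shows how pooling can add separation.

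**4. Enumeration.** One binary covariate, four levels, 0 to 2 patients per cell, every binary cut. Of 3,312 separated table-and-cut pairs, 2,736 stayed separated, 576 collapsed to one outcome level (not estimable), and 0 were cured. Of 15,840 non-separated pairs, 5,472 became separated. These counts show what is possible; they are not probabilities for this trial.

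**5. How often the SAP trigger would arise.** Datasets were simulated with treatment and the SAP 7.2 covariates, using an assumed Day 28 distribution (A below), regions at 8%, 62% and 30%, and a varying share partially vaccinated. Separation on the full scale:

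| N | Partially vaccinated | Separated |
|---|---|---|
| 610 | 1% | 2 of 150 |
| 610 | 2% | 0 of 150 |
| 60 | 5% | 10 of 400 (2.5%) |
| 30 | 8% | 37 of 400 (9.3%) |

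All 2 + 0 + 10 + 37 = 49 separated datasets stayed separated with six levels and with two.

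**6. Precision at the two-level extreme.** Whitehead variance of the log odds ratio, 1:1 allocation: 12 / [N(1 − Σp³)], with N = 610 (SAP 6). The distributions put 30% at level 1 or below and 40% at level 2, matching the placebo rates of 30% and 70% in Protocol 8.1. The split within these groups and over the remaining levels is assumed.

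- A: .10, .20, .40, .08, .08, .05, .02, .02, .05
- B: .10, .20, .40, .20, .03, .02, .01, .01, .03
- C: .10, .20, .40, 0, .14, .06, .02, .02, .06

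| | 1 − Σp³, full | 1 − Σp³, two levels | SE full | SE two levels | Variance ratio |
|---|---|---|---|---|---|
| A | 0.9257 | 0.5148 | 0.146 | 0.195 | 1.80 |
| B | 0.9189 | 0.2700 | 0.146 | 0.270 | 3.40 |
| C | 0.9238 | 0.6300 | 0.146 | 0.177 | 1.47 |

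One assumed Day 7 distribution gives SEs of 0.145 and 0.163, a variance ratio of 1.27.

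**7. Milder pooling.** In A, merging levels 6 to 8 (.02 + .02 + .05 = .09) changes Σp³ from 0.0743 to 0.0749. The information kept is 0.9251 / 0.9257 = 99.9%.

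**8. The unequal-slopes check.** SAP 9.3.2.3 also refits the model with a separate treatment slope at each cut-point. There, level 8 empty in one arm does cause separation, and merging 7 with 8 removes it.

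**The case against.** The case for leaving the rule alone has real weight.

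- Pooling is optional and conditional. The SAP says levels may be pooled, two levels is a floor, and the trigger is separation already present on the full scale. A reader might infer that the plan sends the endpoint to a binary comparison, or that pooling will often create separation in this trial. The SAP does not support either: datasets that fit on the full scale are not pooled under its rule. The protocol's low-frequency trigger is wider, but it names no two-level cut.
- A reader might also infer that the ITT analysis stands to lose the precision in step 6. That needs separation in about 610 patients and then pooling to the limit. Step 5 suggests the first is rare, and step 7 shows that stopping short of the limit costs little.
- Remedies that can work are already there: dropping the covariate (9.3.2.3) and merging regions (7.5).
- Pooling has a proper use in the unequal-slopes check.
- Subgroup analyses are declared exploratory. Every OSCI level is tabulated at each post-baseline visit, and severe disease, intubation and death are analysed separately, so the distinction between oxygen and death is not lost from the report.

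These points limit the consequences. They do not rescue the clause: for the main model it prescribes a step that cannot achieve its stated purpose.

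**Conclusion.** The point holds, with modest impact. That pooling cannot cure separation is algebra and rests on no assumed data. The variance inflation of about 1.5 to 3.4 (standard error about 1.2 to 1.8 times larger) rests on assumed Day 28 distributions, ignores covariates, and applies only at the two-level extreme. The expectation that the trigger is rare in the ITT population and more plausible in small subgroups rests on assumed covariate frequencies.

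The analysis lies outside the testing sequence in SAP 7.6, so no confirmatory claim depends on it. The rule should still be changed, because it names the wrong cause, offers an ineffective remedy, and is inconsistent with the Firth rule for the neighbouring binary endpoints.

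**What to change.** In SAP 9.3.2.3, for the main equal-slopes model, remove outcome pooling as the response to separation and keep all observed OSCI levels at every visit. If separation is flagged:

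1. combine the sparse covariate level with a neighbour, as SAP 7.5 already allows for Latin America and India;
2. if that is not enough, drop that covariate, as 9.3.2.3 already allows;
3. alternatively, use a penalised (Firth-type) proportional-odds fit.

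Apply the same choice across all visits, as 9.3.2.1 does for Firth. Keep level pooling only for the unequal-slopes check of proportionality, and align the merging sentence in Protocol 8.5.3.

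The cost is a paragraph of SAP wording, a matching protocol sentence, and a little programming if the penalised ordinal fit is chosen. No new data are needed.
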